8.0 Study Endpoints

- The primary endpoint is the Overall Response Rate (ORR), defined as partial or complete response (per irRECIST) within 6 months of initiating combination therapy.
- The secondary endpoint is time to tumor progression (TTP), measured from the date of

study enrollment to the first observation of progressive disease.

- Exploratory endpoints: Pre-treatment levels of immunosuppressive cells and the functional activity of effector T cells will be compared to post-treatment blood and tumor samples and will be correlated with overall survival.

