the first 3 weeks of combination therapy (a medication diary will be provided during this time to monitor participant compliance: see Appendix F). All toxicities will be assessed upon completion of the first 6 evaluable patients to see if any higher than anticipated occurrence of sorafenib toxicity is seen due to the addition of pembrolizumab.

The goal of the study is to evaluate efficacy of the combination therapy, therefore patients who are removed from the study prior to receiving the soraf+pembro combination treatment will be replaced. This includes replacing patients who do not tolerate sorafenib alone, as administered in the 1st 4 - 6 weeks of the treatment regimen. In addition, the following patients will be replaced:

- Patient withdraws consent
- Withdrawal from study due to toxicity,
- Withdrawal from study due to liver failure
- Patients who withdraw before the Week 12 (± 1 week) response assessment (for reasons other than progression)

Patients who withdraw due to disease progression prior to the Week 12 (± 1 week) response assessment of the combination therapy will not be replaced and will be counted as non-responders in the response rate calculations.

Patients who complete the 4-6 week initial treatment with sorafenib alone, and withdraw from the study after being treated with the combination therapy will not be replaced and will be counted as non-responders in the response rate calculations.

Patients will receive sorafenib + pembrolizumab until progression. If a patient discontinues either agent due to toxicity, they will still be able to stay on study until progression. Clinical benefit will be considered when making decision to stop therapy as radiographic reflection of true failure of this combination is still unknown.

Disease assessment (imaging) will be done every 6 weeks from the start of C1D1 combination therapy, with a confirmatory assessment no less than 6 weeks after an irPR or irCR or irPD. Therapy will be continued until the confirmatory scan, even if progression is noted on the Week 12 scan. After the 12-week scan disease assessment will be done every 9 weeks (± 1 week). Note: Timing for assessing ORR in patients on immunotherapies is not clear. Disease stability is the commonly seen response to sorafenib alone. Allowing continuation until the confirmatory scan at Week 18, even if progression is seen, allows us to assess the true response to this novel combination.

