19.0 Statistical Plan

Primary interest is in the Overall Response Rate (ORR) related to sorafenib + pembrolizumab combination therapy in advanced stage HCC patients. The ORR is defined as the proportion of evaluable patients who attain either complete or partial response (by irRECIST) within 6 months of initiating combination therapy. Our working hypothesis is that sorafenib + pembrolizumab will increase the ORR by at least 15 percentage points over the standard of care (where responses are rare ~2-3%).

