19.1 Sample Size Determination

Proposed is a one-stage, single arm, unblinded Phase II trial. ORR for patients receiving the standard of care therapy is around 0.05. An exact one-stage design proposed by Kepner and Chang tests the null hypothesis that the proposed treatment has an ORR that is equal to the

Roswell Park Protocol No.: I 35316

standard of care, against an alternative that it is greater. The design has 80% power to detect an ORR of 0.20 or greater with the study treatment, while controlling to 5% the nominal probability of erroneously finding a truly ineffective treatment as worthy of further research (21, 22).

The first 6 patients will comprise the Phase 1b safety lead-in. If ≥ 2 of these patients experience an unexpected, treatment related toxicity of grade ≥ 3 during the first cycle of therapy, the study will be stopped to reevaluate dosing. We anticipate that such limiting toxicities will be observed in ≤ 1 of the first 6 patients. All evaluable patients who receive the Phase 2 dose will be included in the Phase 2 study.

We expect 27 evaluable patients will be enrolled on the trial. If 4 or more of the 27 evaluable patients achieve complete or partial response, the treatment will be deemed effective and considered for further study.

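### Section 9.1 gives two conflicting rules for combination-treated patients who withdraw from the study without progression, so the make-up of the 27 patients in the 4-of-27 decision is contradictory

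*Combined protocol and SAP*

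**What the plan says.** Section 9.1 first gives a reason for replacement: the aim is to evaluate the combination, so "patients who are removed from the study prior to receiving the soraf+pembro combination treatment will be replaced". It then adds a further list of patients to be replaced:

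- those who take back their consent;
- those who leave because of toxicity, worded as "Withdrawal from study due to toxicity";
- those who leave because their liver fails, in matching words;
- those who leave early without progressing, given as "Patients who withdraw before the Week 12 (± 1 week) response assessment (for reasons other than progression".

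The first three items carry no time limit. Patients who progress before Week 12 are not replaced and count as non-responders. A separate sentence then covers patients who complete the sorafenib lead-in and "withdraw from the study after being treated with the combination therapy will not be replaced and will be counted as non-responders". It has no limit by time or reason.

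The only stated criterion for being evaluable is also in Section 9.1: more than 75% of prescribed sorafenib during the first three weeks of combination therapy. Sections 9.1 and 19.1 both say that evaluable patients who receive the Phase 2 dose are included in the Phase 2 study.

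Section 8.0 gives the primary endpoint as response rate, "defined as partial or complete response (per irRECIST) within 6 months of initiating combination therapy". Section 19.0 sets the denominator: "The ORR is defined as the proportion of evaluable patients who attain either complete or partial response". Section 19.1 sets the decision: "If 4 or more of the 27 evaluable patients achieve complete or partial response, the treatment will be deemed effective". Section 19.3 again uses evaluable patients. None of these states how withdrawn patients are handled. Section 4.0 plans 41 accrued, with at most 27 evaluable.

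**The concern.** Take a patient who completes the lead-in, starts the combination, takes enough sorafenib to be evaluable, and withdraws from the study for toxicity in week 8 without progression. The replacement list removes this patient from the 27 and brings in another. The later sentence keeps the patient as a non-responder. Both cannot apply.

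This affects the trial's only efficacy decision. Under replacement, the result describes patients who stay on study, not everyone who received the combination. Under counting, it describes all treated patients, but the planned power holds only if 0.20 was meant for that group. The trial is open-label, so a choice made once responses are known could settle the outcome.

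There is a secondary wording point. Read literally, the later sentence also turns a patient with a documented response who later withdraws into a non-responder. That conflicts with the endpoint in Sections 8.0 and 19.0, which asks only for a response within six months.

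**Working it through.** **Inputs.** From Section 19.1: null rate 0.05, alternative 0.20, 80% power, 5% error, n = 27, success at 4 or more responders. From Section 19.0: standard-of-care responses of about 2-3%. From Section 4.0: 41 accrued. Assumed, because the documents give no figure: a share f of combination-treated patients who withdraw early without progression, set at 5%, 10%, 20% and 30%, all taken as non-responders.

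**The plan's own figure.** With X binomial(27, p), P(X ≥ 4) is 0.0437 at p = 0.05 and 0.8177 at p = 0.20. The stated error and power are reproduced.

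**Each rule with 27 analysed.**

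- Replacement: if p is the rate in all treated patients, the rate among the 27 who stay is p/(1−f).
- Counting: if p is the rate among patients who stay, the rate among the 27 treated is p(1−f).

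| f | Replacement, P(X ≥ 4), all-treated rate 0.05 | Replacement, all-treated rate 0.03 | Counting, power, stayers' rate 0.20 | Counting, P(X ≥ 4), stayers' rate 0.05 |
|---|---|---|---|---|
| 5% | 0.0512 | 0.0098 | 0.7822 | 0.0373 |
| 10% | 0.0602 | 0.0117 | 0.7420 | 0.0315 |
| 20% | 0.0849 | 0.0174 | 0.6471 | 0.0215 |
| 30% | 0.1231 | 0.0269 | 0.5346 | 0.0138 |

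Example at f = 20%: 0.05/0.80 = 0.0625 gives 0.0849, and 0.20 × 0.80 = 0.16 gives 0.6471.

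The other two combinations keep the planned figures. If 0.05 and 0.20 refer to patients who stay, replacement keeps 0.0437 and 0.8177. If they refer to all treated patients, counting keeps them.

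**How plausible f is.** To obtain 27 who stay at f = 30%, 27/0.70 = 38.6 patients must be treated. That leaves about 2.4 of the 41 for all lead-in losses, so 30% is an extreme.

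**At the boundary.** Suppose 3 of the first 27 treated respond and k others withdraw early without progression. Counting gives 3/27 = 11.1%, not effective. Replacement adds k patients and reaches 4/27 = 14.8% if at least one responds, with chance 1 − (1−p)^k:

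- k = 1: 5% at p = 0.05, 20% at p = 0.20
- k = 2: 10% and 36%
- k = 3: 14% and 49%

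**If replacements are already enrolled.** Counting the withdrawn patients as well would push the denominator above 27. With 4 responders and 6 such patients the result is 4/33 = 12.1%, and P(X ≥ 4) at 0.05 with n = 33 is 0.081. The plan has no decision rule for 33.

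**The case against.** The best defence is a sequential reading: replace before the combination; replace before Week 12 without progression; count progression before Week 12 as non-response; count any later withdrawal as non-response. This removes much of the clash and may be what was intended. But the later sentence is not limited to withdrawals after Week 12, and the consent, toxicity and liver-failure items are not limited to before it, so those three would still overlap with it after Week 12. Nor can the list be confined to patients who never reached the combination: it is introduced as an addition to them, and Week 12 is counted from the start of combination therapy.

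A second defence is that evaluability is defined, by the 75% sorafenib criterion. This stands in part: a patient who stops sorafenib very early may be non-evaluable whichever rule applies. A reader might therefore go too far in inferring that the plan gives no definition at all. However, the criterion concerns early exposure, sits beside the safety lead-in text, does not say what happens to a patient who meets it and then withdraws, and is not carried into Section 19.

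A third is that the numbers may be small. Section 9.1 lets patients who stop either agent for toxicity stay on study, so stopping a drug is not withdrawal from the study. If p is the rate among patients who stay, the replacement set has at least as many responders as the counting set, so the chance that the rules disagree is the difference between their success probabilities. From 5% to 30% withdrawal, that is 0.6 to 3.0 percentage points at a rate of 0.05 and 3.6 to 28 points at 0.20. This limits the size of the problem but does not remove it.

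**Conclusion.** The contradiction is real and must be resolved before the primary analysis. At assumed withdrawal of 5% to 20%, replacement raises the chance of a positive decision from 4.4% to between 5.1% and 8.5% when the all-treated rate is 5%. Counting lowers power from 82% to between 78% and 65% if 0.20 is the rate among patients who stay. The 30% figures (12.3% and 53%) are an extreme. All of these rest on assumed shares and on withdrawn patients being non-responders.

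Three stronger inferences are not supported. The sample size and cut-off are not wrong; they reproduce. Type I error is not inflated in general: it stays at 0.044 for patients who stay, and if the all-treated rate is 3%, within the range in Section 19.0, replacement stays below 5% throughout. And it is not assured that either rule ends with exactly 27 patients, because replacements may already be enrolled when withdrawals are counted. The loss of a documented responder is a secondary wording defect, since Sections 8.0 and 19.0 point the other way.

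**What to change.** Reconcile Sections 9.1 and 19.0 to 19.3 to one rule for the primary response analysis only, fixed before responses are analysed. Leave replacement for the safety lead-in as it is. State whether the 75% sorafenib criterion applies to the response set or only to the lead-in. Either option below is coherent; the sponsor should choose one.

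**Option 1, count.** The response set is the first 27 patients, in order of starting the combination, who receive at least one dose of it; the 75% criterion is limited to the lead-in. A patient without irCR or irPR within six months, for any reason, is a non-responder. A response that meets the criteria before withdrawal counts. The rate excluding early non-progression withdrawals is a sensitivity analysis.

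**Option 2, replace.** Keep the replacement list and put a time limit on the consent, toxicity and liver-failure items. Limit the non-responder sentence to withdrawals that the list does not cover and to patients without an earlier qualifying response. Say that the 4-of-27 decision applies only to patients who stay on study, and report the response rate in all combination-treated patients beside it.

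Under either option, state which population the 0.05 and 0.20 rates describe, and restate the power if 0.20 does not refer to the analysed set.

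The cost is amendment wording, with no new data. The reported response rate or the stated power may be lower.

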10.0 Treatment

Dosing and Administration

1 cycle = 3 weeks of combination therapy

10.1 Sorafenib

During the first 4-6 weeks following enrollment (Days -28 to -1 or Days -42 to -1) patient will be on sorafenib alone.

The recommended daily dose of sorafenib is 800mg (2 x 200mg tablets taken twice daily) without food (at least 1 hour before or 2 hours after a meal.) However, the starting dose may be adjusted at the discretion of the treating physician based on clinical assessment of the patient

Roswell Park Protocol No.: I 35316

during screening with a minimum dose of sorafenib at 200mg BID.

All patients should report to clinic for toxicity evaluation 2 weeks after starting sorafenib.

NOTE: Management of suspected adverse drug reactions may require temporary interruption and/or dose reduction of sorafenib therapy. However, the sorafenib lead-in phase should not extend to greater than 6 weeks from the start of sorafenib to the start of pembrolizumab (For example: Patient develops toxicity 2 weeks after starting sorafenib, which requires a dose hold for 1 week, then re-starts sorafenib with a dose reduction. That patient must be stable on the new dose for at least 1 week before starting pembrolizumab. In this case, the sorafenib lead-in phase is 5 weeks which is in the acceptable window of 6 weeks from start of sorafenib to start of pembrolizumab). Patients will continue to take sorafenib (po), BID, during each 3-week cycle.

10.1.1 Dose Modifications for Suspected Adverse Drug Reactions

- Temporary interruption of sorafenib is recommended in patients undergoing major surgical procedures (refer to package insert).

10.1.2 Dose Modifications for Hepatic Impairment at Baseline

- Mild to moderate (Child-Pugh class A and B) impairment: No dosage adjustment is necessary.

The following adjustments have also been reported:

Safety and pharmacokinetics were studied in varying degrees of hepatic dysfunction with the following empiric dose levels recommended based on patient tolerance (Miller, 2009) (12):

- *Mild hepatic dysfunction* (bilirubin >1 to \leq 1.5 times ULN and/or AST >ULN):
 - 400 mg twice daily
- *Moderate hepatic dysfunction* (bilirubin >1.5 to \leq 3 times ULN; any AST):
 - 200 mg twice daily
- *Severe hepatic dysfunction:*
 - Bilirubin >3 to 10 x ULN (any AST): 200 mg every 3 days was not tolerated
 - Albumin <2.5 g/dL (any bilirubin and any AST): 200 mg once daily

Drug-induced liver injury during treatment:

- Unexplained (e.g., not due to viral hepatitis or progressive underlying malignancy) significantly increased transaminases:
 - Discontinue treatment

10.1.3 Suggested Dose Modifications for Dermatologic Toxicities

- If Stevens-Johnson syndrome or toxic epidermal necrolysis is suspected, discontinue therapy.

Refer to Appendix I for suggested dose modifications for dermatologic toxicities in patients with hepatocellular carcinoma.

10.2 Pembrolizumab

Starting with Cycle 1, treatment with pembrolizumab will be administered on Day 1 of each 3-week treatment cycle, after all procedures and assessments have been completed (as detailed on the Schedule of Procedures: Appendix E).

Pembrolizumab will be administered at a fixed dose of 200 mg, using a 30-minute IV infusion. Sites should make every effort to target infusion timing to be as close to 30 minutes as possible. However, given the variability of infusion pumps from site to site, a window between -5 minutes and + 10 minutes is permitted (i.e., infusion time is 30 minutes -5 min and + 10 min).

The Pharmacy Manual contains specific instructions for the preparation of the pembrolizumab infusion and administration of infusion solution.

Toxicities will be assessed upon completion of the first 6 evaluable patients to see if any higher than anticipated occurrence of sorafenib toxicity is seen due to the addition of pembrolizumab.

Reported adverse events (AEs) and potential risks are described in Section 13. Appropriate dose modifications are described in Table 1 (see **Appendix F**).

Pembrolizumab Dose Modifications

Adverse events (both non-serious and serious) associated with pembrolizumab exposure may represent an immunologic etiology. These adverse events may occur shortly after the first dose or several months after the last dose of treatment. Pembrolizumab must be withheld for drug-related toxicities and severe or life-threatening AEs as per Table 1 (**Appendix F**).

Dosing interruptions are permitted in the case of medical / surgical events or logistical reasons not related to study therapy (e.g., elective surgery, unrelated medical events, patient vacation, and/or holidays). Participants should be placed back on study therapy within 3 weeks of the scheduled interruption. The reason for interruption should be documented in the patient's study record.

Management and dose modifications associated with the above AEs are outlined in **Appendix F**.

10.3 General Concomitant Medications

Medications or vaccinations specifically prohibited in the exclusion criteria are not allowed during the ongoing trial. If there is a clinical indication for one of these or other medications or vaccinations specifically prohibited during the trial, discontinuation from trial therapy or vaccination may be required. The final decision on any supportive therapy or vaccination rests with the primary investigator and/or the subject's primary physician.

Acceptable Concomitant Medications

All treatments that the investigator considers necessary for a patient's welfare may be administered at the discretion of the investigator in keeping with the community standards of medical care. All concomitant medication will be recorded on the case report form (CRF) including all prescription, over-the-counter (OTC), herbal supplements, and IV medications and fluids. If changes occur during the trial period, documentation of drug dosage, frequency, route, and date may also be included on the CRF.

All concomitant medications received within 28 days before the first dose of trial treatment and 30 days after the last dose of trial treatment should be recorded. Concomitant medications

Roswell Park Protocol No.: I 35316

administered after 30 days after the last dose of trial treatment should be recorded for SAEs and ECIs as defined in Section 17.0.

Prohibited Concomitant Medications

Patients are prohibited from receiving the following therapies during the Baseline and Treatment Phase of this study:

- Antineoplastic systemic chemotherapy or biological therapy
- Immunotherapy not specified in this protocol
- Chemotherapy not specified in this protocol
- Investigational agents other than pembrolizumab
- Radiation therapy
 - *Note:* Radiation therapy to a symptomatic solitary lesion or to the brain may be allowed at the investigator's discretion.
- Live vaccines within 30 days prior to the first dose of trial treatment and while participating in the trial. Examples of live vaccines include, but are not limited to, the following: measles, mumps, rubella, varicella/zoster, yellow fever, rabies, BCG, and typhoid vaccine.
- Anti-viral medications for treatment of hepatitis C while receiving combination therapy
 - *Note:* Patients may continue on anti-viral medication for hepatitis C during the 4-week sorafenib-only therapy.
- Systemic glucocorticoids for any purpose other than to modulate symptoms from an event of clinical interest of suspected immunologic etiology. The use of physiologic doses of corticosteroids may be approved.

Patients who, in the assessment by the investigator, require the use of any of the aforementioned treatments for clinical management should be removed from the trial. Patients may receive other medications that the investigator deems to be medically necessary.

10.4 Rescue Medications & Supportive Care

10.4.1 Supportive Care Guidelines

Patients should receive appropriate supportive care measures as deemed necessary by the treating investigator. Suggested supportive care measures for the management of adverse events with potential immunologic etiology are outlined below. Where appropriate, these guidelines include the use of oral or intravenous treatment with corticosteroids as well as additional anti-inflammatory agents if symptoms do not improve with administration of corticosteroids. Note that several courses of steroid tapering may be necessary as symptoms may worsen when the steroid dose is decreased. For each disorder, attempts should be made to rule out other causes such as metastatic disease or bacterial or viral infection, which might require additional supportive care. The treatment guidelines are intended to be applied when the investigator determines the events to be related to pembrolizumab.

Note: if after the evaluation the event is determined not to be related, the investigator does not

Roswell Park Protocol No.: I 35316

need to follow the treatment guidance (as outlined below). Refer to **Appendix F** for dose modification.

It may be necessary to perform conditional procedures such as bronchoscopy, endoscopy, or skin photography as part of evaluation of the event.

Pneumonitis:

- For Grade 2 events, treat with systemic corticosteroids. When symptoms improve to Grade 1 or less, steroid taper should be started and continued over no less than 4 weeks.
- For Grade 3-4 events, immediately treat with intravenous steroids. Administer additional anti-inflammatory measures, as needed.
- Add prophylactic antibiotics for opportunistic infections in the case of prolonged steroid administration.

Diarrhea/Colitis:

Subjects should be carefully monitored for signs and symptoms of enterocolitis (such as diarrhea, abdominal pain, blood or mucus in stool, with or without fever) and of bowel perforation (such as peritoneal signs and ileus).

- All subjects who experience diarrhea/colitis should be advised to drink liberal quantities of clear fluids. If sufficient oral fluid intake is not feasible, fluid and electrolytes should be substituted via IV infusion. For Grade 2 or higher diarrhea, consider GI consultation and endoscopy to confirm or rule out colitis.
- For Grade 2 diarrhea/colitis, administer oral corticosteroids.
- For Grade 3 or 4 diarrhea/ colitis, treat with intravenous steroids followed by high dose oral steroids.
- When symptoms improve to Grade 1 or less, steroid taper should be started and continued over no less than 4 weeks.

Type 1 diabetes mellitus (if new onset, including diabetic ketoacidosis [DKA]) or \geq Grade 3 Hyperglycemia, if associated with ketosis (ketonuria) or metabolic acidosis (DKA)

- For **T1DM** or **Grade 3-4** Hyperglycemia
 - Insulin replacement therapy is recommended for Type I diabetes mellitus and for Grade 3-4 hyperglycemia associated with metabolic acidosis or ketonuria.
 - Evaluate patients with serum glucose and a metabolic panel, urine ketones, glycosylated hemoglobin, and C-peptide.

Hypophysitis:

- For Grade 2 events, treat with corticosteroids. When symptoms improve to Grade 1 or less, steroid taper should be started and continued over no less than 4 weeks. Replacement of appropriate hormones may be required as the steroid dose is tapered.
- For Grade 3-4 events, treat with an initial dose of IV corticosteroids followed by oral corticosteroids. When symptoms improve to Grade 1 or less, steroid taper should be started and continued over no less than 4 weeks. Replacement of appropriate hormones

may be required as the steroid dose is tapered.

Hyperthyroidism or Hypothyroidism:

Thyroid disorders can occur at any time during treatment: Monitor patients for changes in thyroid function (at the start of treatment, periodically during treatment, and as indicated based on clinical evaluation) and for clinical signs and symptoms of thyroid disorders.

- **Grade 2** hyperthyroidism events (and **Grade 2-4** hypothyroidism):
 - In hyperthyroidism, non-selective beta-blockers (e.g. propranolol) are suggested as initial therapy.
 - In hypothyroidism, thyroid hormone replacement therapy, with levothyroxine or liothyroinine, is indicated per standard of care.
- **Grade 3-4** hyperthyroidism
 - Treat with an initial dose of IV corticosteroid followed by oral corticosteroids. When symptoms improve to Grade 1 or less, steroid taper should be started and continued over no less than 4 weeks. Replacement of appropriate hormones may be required as the steroid dose is tapered.

Hepatic:

In addition to overdose (see Section 32.1.6), hepatic events of clinical interest will include any of the following events (see Appendix J: Guidance for Diagnosis and Management of Hepatic Events of Clinical Interest). All of these events will require holding study treatment and, notification to Merck within 2 days.

Refer to Section 17.4 for reporting guidelines and the definition of hepatic events of clinical interest.

Renal Failure or Nephritis:

- For Grade 2 events, treat with corticosteroids.
- For Grade 3-4 events, treat with systemic corticosteroids.
 - When symptoms improve to Grade 1 or less, steroid taper should be started and continued over no less than 4 weeks.

Management of Infusion Reactions: Signs and symptoms usually develop during or shortly after drug infusion and generally resolve completely within 24 hours of completion of infusion.

Table 2 (Appendix G) shows treatment guidelines for subjects who experience an infusion reaction associated with administration of pembrolizumab.

